5.2.1 Discontinuation of Study Treatment

Discontinuation of study treatment and resumption of previous antiretroviral therapy is recommended if:

- Subject experiences virologic failure (defined as two consecutive HIV-1 RNA levels of ≥ 400 copies/ml separated by at least 3 days)
- Develops retroviral rebound syndrome or AIDS-defining conditions as specified in Appendix I ([Section 17.1](#)).
- Shows signs or symptoms of clinically significant immunosuppression
- Subject or the subject's clinician wishes to restart ART.
- Subject becomes pregnant.

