1.7 RISKS / BENEFITS ASSESSMENT

1.7.1 RISKS/DISCOMFORT TO SUBJECTS AND PRECAUTIONS TO MINIMIZE RISK

1.7.1.1 Risks associated with Temporary Discontinuation of current Antiretroviral Treatment Regimen

The study treatment (PRO 140 monotherapy) may not be effective in maintaining the viral suppression for all subjects. In such cases, temporary discontinuation of antiretroviral therapy could lead to a rebound in viral load and might be associated with an increase risk of developing drug resistance, opportunistic infections and clinical progression of the disease.

Study participants will be regularly monitored for viral rebound following initiation of PRO 140 monotherapy and will re-initiate their previous antiretroviral regimen if plasma HIV-1 RNA levels rise up to or above 400 copies/ml on two consecutive blood draws at least 3 days apart.

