4.2 TREATMENT EXTENSION PHASE

Treatment Extension Phase begins with an evaluation of results of laboratory samples collected during the Screening Phase. Subjects who meet all eligibility criteria, as per data gathered from Screening Phase are to be treated. All subjects who fail to meet eligibility criteria will be considered screen failures, exit the study without further evaluation and enter the Follow-up Phase of the PRO 140_CD 01 Treatment Substitution protocol.

Eligible subjects will receive PRO 140 weekly SC treatments, given every week (\pm 3 days) or until virologic failure, whichever occurs first.

PRO 140 will be administered as a 350 mg subcutaneous injection weekly. The study treatment (PRO 140 SC injections) will be administered by a qualified medical professional (MD, DO, PA, LPN, LVN, NP, RN, or CMA if permitted by state law) or subjects trained to perform self-administration of study treatment (see [section 6.4](#)).

Note: Patients enrolled under a previous Protocol (V.1.0-9.0) have the option of increasing their dose to receive 700mg weekly for the remainder of the Treatment Extension Phase.

All study subjects will re-initiate their previous antiretroviral regimen:

- One week prior to the end of Treatment Extension Phase, or
- Anytime during the Treatment Extension Phase, if virologic failure occurs or have met any other criteria for discontinuation of study treatment as specified in [section 5.2.1](#) of the protocol.

Note:

- In case of increase in plasma HIV-1 RNA levels above 200 copies/mL, subjects will return to clinic for another blood draw in-between the Treatment Visits for repeat plasma HIV-1 RNA levels, as per the discretion of the Investigator.
- Subjects who experience virologic failure (defined as two consecutive HIV-1 RNA levels of \geq 400 copies/ml separated by at least 3 days) at any time during the Treatment Extension Phase will undergo the Virologic Failure (VF) Visit assessments and enter the Follow-up Phase of the study.
- Subjects who meet any criteria (other than virologic failure) for discontinuation of study treatment as specified in [section 5.2.1](#) of the protocol, will undergo TE161 Visit assessments and enter the Follow-up Phase of the study.
- Subjects who do not experience virologic failure will enter the Follow-up Phase of the study at the end of 161-week Treatment Extension Phase.

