4.2.3 Treatment Visit-60 (TE60) onwards – Monthly Visits

Patients are required to have a clinic visit at least once every four weeks from TE60 onwards. Subjects will re-initiate previous antiretroviral regimen at end of treatment extension phase (one week prior to last PRO 140 treatment), if viral load remain suppressed.

The following assessments will be performed at every clinic visit:

- Assess for any Adverse Events and changes in Concomitant medications (see [section 9](#) and [7.5](#)),
- Symptom-directed physical examination (see [section 7.6](#)),
- Neurological Assessment (see [section 7.7](#))
- Vital Signs (see [section 7.9](#))
- **Note:** *Vitals not obtained when subject self-administers study treatment outside clinic*
- Study Treatment Administration (PRO 140)
- **Note:** *Subjects trained to perform self-administration of study treatment may self-administer when clinic visit not required (no lab sample collection needed)*

- Injection Site Reaction Assessment (see [section 7.12](#))
 - **Note:** *To assess injection site reactions, the investigator will use the DAIDS AE grading table (see [section 17.3](#)).*
 - **Note:** *Assessment will be performed when subject administered study treatment at clinic visit*
- Subject-perceived Injection Site Pain Assessment (see [section 7.13](#))
 - **Note:** *Subject-perceived injection site pain will be assessed using the Pain Visual Analog Scale (VAS) prior to study treatment administration assessing average pain at injection site since last treatment.*
 - **Note:** *Performed at the time of clinic visit.*
- Collection of Blood Specimens (see [section 7.10](#)) for
 - Plasma HIV-1 RNA level
 - TruCount T Assay
 - Routine CBC
 - Biochemistry
 - PK sample for PRO 140
 - Serum concentration of ART drugs
 - Anti-idiotypic antibodies to PRO 140
 - Blood sample for exploratory analysis
- **Note:** *Trofile® RNA or Trofile® DNA and PhenoSense Entry Assay will be performed at the last treatment visit (EOT)*
 - CCR5 Receptor Occupancy
- **Note:** *Blood will be taken prior to PRO 140 injection (trough sample) and 24-48 hours (peak sample) after the PRO 140 injection to check for CCR5 occupancy, and correlative analysis will be performed with PRO 140 PK concentration and HIV-1 RNA levels. This assessment will be performed up to 5 times at different treatment visits.*

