7.14 COVID-19 GUIDANCE

The purpose of this guidance is to inform sites how to proceed in light of the challenges faced by patients and clinical trial sites as a result of COVID-19 shelter-in-place mandates from state governments. The content of this letter is based on FDA Guidance on Conduct of Clinical Trials of Medical Products during COVID-19 Pandemic (18 Mar 2020).

- The current schedule of assessments requires subjects to visit the clinic at least once every four weeks for lab assessments. Subjects may still continue to receive treatment with PRO 140 if they are unable to visit the clinic.
- Site staff may visit subjects' homes to conduct study assessments and/or deliver PRO 140.
- Sites may ship PRO 140 to subjects' homes if subjects are unable to visit the clinic.
- If subjects are unable to visit the clinic at least once every four weeks lab assessments will be missed. If this occurs site staff should contact subjects weekly by phone to assess:
 - Compliance to study treatment
 - Potential adverse events
 - Changes in concomitant medications
- Sites should document phone calls and include confirmation of compliance to study treatment and report any adverse events and/or changes in medications.
- Subjects who report positive tests results for COVID-19 should have the diagnosis recorded as an adverse event.
- Sites should clearly document reasons for failing to obtain required assessments (e.g., limitation imposed by COVID-19 leading to the inability to perform the protocol-specified assessment).

- Any changes in the study visit schedule or missed visit should be entered as protocol deviation in the EDC and reason should be documented as missed study visit or visit performed out of window period due to COVID-19.
- If subject is early withdrawn from the study due to COVID-19, the reason should be clearly documented in the End of Study (EOS) section in EDC as “study discontinuation due to COVID-19”.
- Monitoring activities will be performed remotely until Centers for Disease Control (CDC) recommendations allow travel to resume.

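### Early ART restart without a confirming HIV-1 RNA is routed as a non-failure, so some rebounds may escape both the failure count and the virologic-failure work-up

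*Protocol*

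**What the plan says.** Section 8.2.1 of the protocol recognises one failure event: two consecutive HIV-1 RNA values of at least 400 copies/mL, at least 3 days apart. Section 1.7.1.1 gives the matching restart rule: subjects resume ART if their values "rise up to or above 400 copies/ml on two consecutive blood draws at least 3 days apart".

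Section 5.2.1 adds further grounds for stopping PRO 140 and resuming ART. One reads "Develops retroviral rebound syndrome or AIDS-defining conditions as specified in Appendix I". Another applies when the subject or the subject's "clinician wishes to restart ART". Neither asks for a viral load. Section 7.5.1 permits ART on any Section 5.2.1 ground.

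Section 4.2 then fixes the route: "Subjects who meet any criteria (other than virologic failure) for discontinuation of study treatment as specified in" Section 5.2.1 have the TE161 assessments and move to follow-up. After a value above 200 copies/mL the subject comes back "for repeat plasma HIV-1 RNA levels, as per the discretion of the Investigator". Subjects who fail "at any time during the Treatment Extension Phase will undergo the Virologic Failure (VF) Visit assessments", which leads to the failure branch of Table 4-9.

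**The concern.** The exit rules are wider than the event definition, and the visit route follows the exit label rather than the viral load. A subject can rebound on monotherapy, go back on ART, and be handled throughout as a non-failure because no valid second sample exists.

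Two things are at stake. The first is safety follow-up: the non-failure branch does not require the resistance work-up or the confirmation of re-suppression that the protocol gives to failures. The second is the secondary endpoint in Section 8.2.2, the proportion with virologic failure. An uncounted rebound lowers it, in favour of PRO 140, in a study whose stated objective is long-term efficacy.

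**Working it through.** The protocol states no figure on this point, so there is none to reproduce. The check traces the route and then sizes one case.

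**Sampling around an exit**
- Section 7.10.6: RNA is drawn at even-numbered visits to TE58, so every 2 weeks, and at least every 4 weeks beyond TE60. Section 4.2.3 agrees: "Patients are required to have a clinic visit at least once every four weeks from TE60 onwards".
- Section 7.14: "If subjects are unable to visit the clinic at least once every four weeks lab assessments will be missed". The same section lets site staff do assessments at home, so a missed draw is possible but not inevitable.
- Table 4-7: TE161 includes one RNA. The table marks the ART regimen at both TE160 and TE161, so in planned use this sample falls after ART has restarted. For early exits no text puts the draw before the restart.
- Table 4-9(a): the next RNA is NVF-EFU1, 14 ± 3 = 11 to 17 days after TE161, on ART. NVF-EFU2 follows at 28 ± 3 = 25 to 31 days.

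**When the two-value definition may not be met**
1. The first value of at least 400 is the exit sample. The preceding routine value may be 2 to 4 weeks old.
2. The repeat is under 3 days after the first, and later values are below 400.
3. ART starts before the second draw.

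In case 1, the drop that takes the NVF-EFU1 value below 400 is log10(V/400): 0.40 log10 from V=1,000, 1.10 from 5,000 and 1.40 from 10,000 copies/mL. The protocol gives no rate of decline on ART, so whether a given rebound is missed is an assumption.

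**What the two routes require**

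| | Failure route | Other early exit |
|---|---|---|
| Visit | VF | TE161 |
| HIV genotyping (7.10.9) | Yes | Not scheduled |
| Trofile, PhenoSense Entry | Yes | Yes |
| Follow-up | Every 4 weeks until below 50 copies/mL | 2 and 4 weeks |
| 12- and 24-month visits | Yes | No |

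**Size per uncounted case**

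The change in the failure proportion is 1/N. N=23 is the number completing CD 01 without failure (Section 1.5.2.7); N=28 is the cap in the synopsis.
- 1/23 = 4.3 points; 1/28 = 3.6 points.
- Two cases (an assumed count): 2/23 = 8.7 points; 2/28 = 7.1 points.

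**The 30-day comparison**

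As a stand-in for the planned rank test, take a two-sided sign test of the median against 30 days, p = 2·P(X ≤ k) with X binomial(N, ½) and k failures before day 30. At N=23, k=6 gives p=0.035 and k=7 gives 0.093. At N=28, k=8 gives 0.036 and k=9 gives 0.087. One or two reclassified subjects would matter only if early failures were already near those counts. Entrants have already gone 12 weeks without failure.

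**The case against.** The design has good reasons behind it. A confirmed endpoint guards against transient elevations, and a symptomatic, pregnant or unwilling subject on monotherapy should be able to restart ART without virologic proof. Both stand, and the fix keeps both.

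Many rebounds will still be confirmed. If a value of at least 400 was already known, TE161 supplies a second sample, and NVF-EFU1 and NVF-EFU2 supply more. Section 8.2.1 sets no phase limit, so a high follow-up value could count. That stands for the endpoint. It does not repair the route, because Section 4.2 sends only failures during the Treatment Extension Phase to the VF visit.

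Other safeguards exist: contact with the medical monitor and continued follow-up where possible (Section 5.2.2), reported reasons for discontinuation (Section 8.7.1), and review of virologic rebounds by the data monitoring committee (Section 12). None secures a confirming sample or moves the subject to the failure branch.

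A reader might infer that such exits inflate a survival curve through informative censoring. The protocol does not support that. Section 8.7.4.1 plans a Wilcoxon test and a median compared with 30 days, and Kaplan-Meier appears only for the historical data in Figure 1-1. Whether an early restart is an event, censored or imputed may also be settled in the SAP, which is not at hand. No effect on a Kaplan-Meier estimate is claimed.

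Finally, one subject is small against sampling error: with an assumed 5 failures in 23, the exact 95% interval runs from 7.5% to 43.7%. That is fair, and it limits the efficacy side of this point.

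**Conclusion.** The gap in routing is real and is fixed in the protocol itself. A subject can restart ART for rebound syndrome, or by choice with a last value of at least 400 copies/mL, and leave with no requirement for genotyping, follow-up to re-suppression or the long-term failure visits. Such a subject may also go uncounted as a failure.

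The numerical effect is 4.3 or 3.6 points on a descriptive proportion for each uncounted case. It assumes that the case stays a non-event in a denominator of 23 or 28, and the number of cases is unknown. It would be too strong to say that rebound-led exits are generally missed, or that the primary comparison is biased: several later samples can confirm a rebound, and the 30-day comparison is little affected.

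**What to change.** 1. In Section 4.2, make a repeat HIV-1 RNA at least 3 days after any value of at least 400 copies/mL mandatory. The repeat for values from above 200 to below 400 can stay discretionary. At any early exit, draw RNA before ART restarts, without delaying ART where it is clinically needed.
2. In Sections 4.2 and 4.3 and Table 4-9, send to the VF visit and VF follow-up branch every subject who restarts ART with a last RNA of at least 400 copies/mL, or for rebound or rebound syndrome. Include those confirmed only in follow-up. This covers subjects whose repeat has to be taken on ART.
3. Keep the confirmed definition as the main endpoint, and also report the failure proportion with these exits counted as failures. If the SAP already does this, nothing need be added there.

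The cost is amendment wording, a few extra draws, and assessments that already exist in the VF schedule, for a small number of subjects. No patients are added. The supportive failure rate may be less favourable and may include transient elevations, which is why it should not replace the confirmed endpoint. Requiring every subject to wait at least 3 days for the repeat before ART would be a trade-off against safety and is not proposed.

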5.2.2 Data Collected for Withdrawn Subjects

Patients may withdraw from the study or discontinue study treatment at any time; however, CytoDyn, Inc. is dedicated to minimizing missing data in this study. It is therefore suggested that all patients, regardless of whether they continue to receive study treatment, continue within the study.

Investigators considering discontinuing study treatment should contact the medical monitor prior to such discontinuation. Patients who have study treatment discontinued will continue to be followed, per protocol, whenever possible. Patients who have study treatment discontinued due to a serious adverse event will be followed until resolution or stabilization of the event.

In the event that a subject is withdrawn from the study at any time due to an adverse event or serious adverse event (SAE), the procedures stated in [Section 9.1.1](#) or [9.3](#), respectively must be followed.

Every attempt should be made to collect follow-up information. The reason for withdrawal from the study will be recorded in the source documents and on the appropriate page of the eCRF.

Before a subject is identified as lost-to-follow up, the site should make all reasonable efforts to contact the subject. These attempts must be documented and should include at a minimum one phone call and one certified letter.

5.3 SCREEN FAILURES

A subject who has signed a consent form, has been assigned a screening number, but is not treated is classified as a screen failure. Subject number, demographics and reason for screen failure will be recorded.

6 STUDY TREATMENT

6.1 INVESTIGATIONAL PRODUCT DESCRIPTION

PRO 140 is a humanized IgG4,κ monoclonal antibody (mAb) to the chemokine receptor CCR5. PRO 140 is provided at a concentration of 175 mg/mL and is intended for SC route of administration.

Kits will be labeled with a unique identification number. Each kit used during Study Treatment will contain vials of PRO 140 for SC injection. Based on the dose administered to the subjects, 1 mL (350 mg dose) or 2 mL (700 mg dose) PRO 140 solution will be drawn from a vial and loaded into the syringe. A total of 350 mg or 700 mg of PRO 140 (from stock concentration 175mg/mL) is delivered as two injections administered subcutaneously on opposite sides of the abdomen or as one of the alternative methods listed in [Section 6.4](#) below. One study injection kit will be assigned per subject per treatment visit (with exception for 350 mg dose with 2.4 mL fill volume in which one kit can be used for two doses).

Table 6-1: PRO140 Dose Administration: Kit Information

PRO 140 Kits Containing 1.4 mL per Vial				
PRO 140 Dose	# of Vials Used per Dose	Total Injection Volume (mL)	Volume (mL) Administered per Injection*	Volume (mL) Discarded per Vial
350 mg	2	2	1	0.4
700 mg	4	4	2	0.4
PRO 140 Kits Containing 2.4 mL per Vial				
PRO 140 Dose	# of Vials Used per Dose	Total Injection Volume (mL)	Volume (mL) Administered per Injection	Volume (mL) Discarded per Vial
350 mg*	1	2	1	0.4
700 mg**	2	4	2	0.4

PRO 140 175 mg/mL will be provided in 3 mL vials containing ~ 2.4 mL of PRO 140 in a sterile buffered solution of 5mM Histidine, 15 mM Glycine, 95 mM Sodium Chloride, 0.3% (w/v) Sorbitol, 0.005% (w/v) Polysorbate 20, at pH of 5.5.

Note: *Since each vial contains 2.4 mL of PRO140, only 1 vial is needed for the 350 mg dose. 2 mL injection will be drawn from ~~4~~2.4 mL solution in a vial. The second vial can be utilized to administer 350 mg dose at the subsequent visit. Remaining 0.4 mL medication will be discarded appropriately from each vial.

Alternatively, when 2.4 mL vials are provided, 2 mL injection will be drawn from each vial and the remaining 0.4 mL medication will be discarded. Unused content of PRO 140 in a vial should remain in the vial and **not be administered to any other subject.

Table 6-2 provides the unit strength, dosing frequency and mode of administration for the study drug.

Table 6-2: Investigational Product - PRO 140

Study Drug	Dosage Form	Dose	PRO 140 concentration	Dosing Frequency and Amount	Route of Administration
PRO 140	Parenteral solution	350 mg	175 mg/mL	Two 1 mL inj. on opposite sides of abdomen Weekly SC doses of PRO 140 (2x1 mL)	SC injection
PRO 140	Parenteral solution	700 mg	175 mg/mL	Two 2 mL inj. on opposite sides of abdomen Weekly SC doses of PRO 140 (2x2 mL)	SC injection

6.2 INVESTIGATIONAL PRODUCT PACKAGING AND LABELING

Study drug will be prepared by Ajinomoto Althea, Inc. and will be packaged, labeled, and shipped by PCI Clinical Services.

The contents of each vial are described in [Section 6.1](#). PRO 140 kits will be labeled with information such as: study protocol #; fill volume; concentration; storage condition; a “use as per study protocol” statement; a cautionary statement; sponsor’s name and address; and the kit number.

Note: PRO 140 kits prepared for Protocol: PRO 140_CD 01 will be used for the extension protocol.

Below are representative samples of the PRO 140 (CHO), 175 mg/mL, FDP individual vial ([Figure 6-1](#)), syringe label ([Figure 6-2](#)), and kit labels ([Figure 6-3](#)) designated for use in this clinical protocol. Each kit contains two labeled vials and two syringe labels.

Figure 6-1: PRO 140 (CHO), 175 mg/mL Vial Label

Vial Label:

Protocol: PRO 140_CD 01	Kit No. xxx	Protocol: PRO 140_CD 01	Kit No. xxx
Subject No. _____		Subject No. _____	
Single use 3 mL vial contains 2.4 mL of PRO 140 (175 mg/mL) solution for subcutaneous injection		Single use 3 mL vial contains 2.4 mL of PRO 140 (175 mg/mL) solution for subcutaneous injection	
Store at 2°C to 8°C (36°F to 46°F)		Store at 2°C to 8°C (36°F to 46°F)	
USE AS PER STUDY PROTOCOL		USE AS PER STUDY PROTOCOL	
Caution: New Drug – Limited by Federal (or United States) Law to Investigational Use		Caution: New Drug – Limited by Federal (or United States) Law to Investigational Use	
CytoDyn Inc., Vancouver, WA, USA		CytoDyn Inc., Vancouver, WA, USA	

Figure 6-2: PRO 140 (CHO), 175 mg/mL Syringe Label

Syringe Label:

Protocol: PRO 140_CD 01	Contents of Kit No. xxx
This syringe contains 1 mL or 2 mL PRO 140 (175 mg/mL) solution for subcutaneous injection	
USE AS PER STUDY PROTOCOL	
Caution: New Drug – Limited by Federal (or United States) Law to Investigational Use	
CytoDyn Inc., Vancouver, WA, USA	

Note: Subjects on 700 mg dose require a total of 4ml of study drug for single dose, given as two 2ml injections, or four 1 mL injections

Figure 6-3: PRO 140 (CHO), 175 mg/mL Kit Label

Kit Label:

Protocol: PRO 140_CD 01	Kit No. xxx
-------------------------	-------------

Site No. _____

Subject No. _____

This kit contains 2 single-use vials

Each 3 mL vial contains 2.4 mL of PRO 140 (175 mg/mL) solution for subcutaneous injection

Store at 2°C to 8°C (36°F to 46°F)

USE AS PER STUDY PROTOCOL

Caution: New Drug – Limited by Federal (or United States) Law to Investigational Use

CytoDyn Inc., Vancouver, WA, USA

The pharmacy manual provides the criteria regarding vial acceptance or rejection, as well as instructions for the preparation of the filled syringes to be used to administer drug.

6.3 INVESTIGATIONAL PRODUCT STORAGE

Study drug will be shipped at 2°C to 8°C (refrigerated [36°F to 46°F]) to the investigator's site. Upon receipt at the site, the responsible site staff or pharmacist should verify the integrity of the vials. Study drug should be stored at 2°C to 8°C (refrigerated [36°F to 46°F]). The contents of the vial should appear as a clear to opalescent, colorless to yellow solution; fine translucent particles may be present. This is normal.

The investigator must maintain an accurate record of the shipment, storage, and dispensing of the study drug in a drug accountability log. An accurate record including the date and amount of study drug dispensed to each subject must be available for inspection at any time. A study CRA assigned to monitor the investigational site will review these documents once study drug has been received by the investigational site. Study drug will be accounted for on an ongoing basis during the study.

